The Effect Of Preoperative Parameters On Success After Descemet Membrane Endothelial Keratoplasty (DMEK) Surgery

CLINICAL STUDY PLAN

ClinicalTrials.gov Results Data Element Definitions for Interventional and Observational Studies

▼ 1. Participant Flow Enrollment Assessed for eligibility (n=) Excluded (n=) $_{\square}$ Not meeting inclusion criteria (n=) □ Declined to participate (n=) □ Other reasons (n=) Allocated to intervention (n=) Received allocated intervention (n=) Did not receive allocated intervention (give reasons) (n=) Follow Up Lost to follow Discontinued intervention (give reasons) (n=) Analysis Analysed (n=) Excluded from analysis (give reasons) (n=)

Groups/Cohorts	Interventions
Cohort	Procedure/Surgery: Descemet membrane endothelial keratoplasty
	(DMEK)
All patients	All participants underwent DMEK surgery

Period(s)

Our study was created by planning a 6-month follow-up period. Information about the number of patients at the beginning and end of the study will be reported when the study is completed.

▼ 2. Baseline Characteristics

Patients' age, gender, eye side, additional diseases, medications used and preoperative visual acuity values will be recorded at the beginning of the study.

Groups/Cohorts	Interventions
Cohort	Procedure/Surgery: Descemet membrane endothelial keratoplasty (DMEK)
All patients	All participants underwent DMEK surgery

Baseline Analysis Population Information

Overall Number of Baseline Participants

A total of 60 participants are planned to participate in the study.

Baseline Measure Information

Patients' age, gender, eye side, additional diseases, medications used and preoperative visual acuity values will be recorded at the beginning of the study.

Baseline Measure Title

The change in the visual acuity and the change in the number of endothelial cells will be the primary outcome of the study.

Study-Specific Measure *\sqrt{\sqrt{Select as many as needed}}

- Age (Select at least one of the following):
 - Age, Continuous: For example mean or median age
- Sex/Gender (Select at least one of the following):
 - Sex: Female, Male
- Race and Ethnicity
 - Race and Ethnicity Not Collected

Measure Type *

Definition: The type of data for the baseline measure. Select one.

• Count of Participants

Measure of Dispersion

Select one.

• Not Applicable (only if Measure Type is "Number", "Count of Participants", or "Count of Units")

Baseline Measure Data *

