When the investigation is completed, information about each baseline measures data will be updated.

Unit of Measure *

Participants, mmHg, micron, millimeter

▼ 3. Outcome Measures

A table of data for each primary and secondary outcome measure by arm (that is, initial assignment of participants to arms or groups) or comparison group (that is,

analysis groups), including the result(s) of scientifically appropriate statistical analyses that were performed on the outcome measure data, if any.

Note: Outcome measure information from the Protocol Section of the record will be copied into the Results Section the first time results are created.

Primary Outcome Measure:

1.Visual Acuity (Snellen)

Change from baseline

[Time Frame: Baseline and after surgery 1, 3, 6, and 12 months] 2.Endothelial Cell density (cells/mm²)

After surgery measurements

[Time Frame: after surgery 1, 3, 6, and 12 months]

Secondary Outcome Measures:

1. Maximum (steepest) and minimum (flattest) keratometry values in the central corneal zone (K values)

Change from baseline

[Time Frame: Baseline and after surgery 1, 3, 6, and 12 months]

2. Anterior chamber depth (mm)

Change from baseline

[Time Frame: Baseline and after surgery 1, 3, 6, and 12 months]

3. Axial Length (mm)

Change from baseline

[Time Frame: Baseline and after surgery 1, 3, 6, and 12 months]

4. Central pachymetry (micron)

Change from baseline

[Time Frame: Baseline and after surgery 1, 3, 6, and 12 months]

5. Intraocular pressure (mmHg)

Change from baseline

[Time Frame: Baseline and after surgery 1, 3, 6, and 12 months]

Other Pre-specified Outcome Measures:

6. Surgical complications

Complications occurring during the surgery will be recorded.

[Time Frame: During surgery]

Groups/Cohorts	Interventions
Cohort	Procedure/Surgery: Descemet membrane endothelial keratoplasty
	(DMEK)
All patients	All participants underwent DMEK surgery

Analysis Population Information

Overall Number of Participants Analyzed

In total, we expect 60 participants to participate in the study.

Type of Units Analyzed

The analysis will be based on participants

Outcome Measure Data Table Measure Type

• Count of Participants

Measure of Dispersion/Precision

• 95% Confidence Interval

Statistical Analyses

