The required sample size was determined by power analysis based on previous studies. [G * Power, Version: 3.1.9.2 Statistical Packages]. Variance analysis (ANOVA) will be used in the statistical analysis of preoperative and postoperative 1st and 6th months, if the measurements show normal distribution in the repeated measurements. Post-hoc Bonferroni test will be used to find out whether there is a difference between the measurements. Friedman test will be used in the statistical analysis of measurements that do not show normal distribution. Wilcoxon test will be used to find out whether there is a difference between the measurements. Pearson and Spearman correlation test will be used in the correlation analysis. For statistical significance p <0.05 will be accepted.

▼ 4. Adverse Event Information

Information for completing three tables summarizing adverse events.

- 1. All-Cause Mortality: Mortality is not expected in our study.
- 2. Serious Adverse Events: Serious adverse event is not expected in our study
- 3. Other (Not Including Serious) Adverse Events: No adverse effects due to study are expected. If any adverse event will be seen, it will be reported.

Time Frame

Adverse event data will be collected between 1 June 2019, and 1 June 2021.

Adverse Event Reporting Description [*]

Patients will be invited to examinations at regular intervals and will contact the researchers at the contact numbers provided if they see any unexpected effects.

Collection Approach for Table Default

• Systematic Assessment: Baseline and after surgery 1, 3, 6, and 12 months

Arm/Group Information

There is only a study group.

Arm/Group Title

All patients

Arm/Group Description

All participants underwent (Descemet membrane endothelial keratoplasty) DMEK surgery

Total Number Affected by All-Cause Mortality

Total Number at Risk for All-Cause Mortality

0

Total Number Affected by Any Serious Adverse Event

Total Number at Risk for Serious Adverse Events

0

Frequency Threshold for Reporting Other (Not Including Serious) Adverse Events

5

Total Number Affected by Any Other (Not Including Serious) Adverse Event Above the Frequency Threshold

Total Number at Risk for Other (Not Including Serious) Adverse Events $\boldsymbol{0}$

Adverse Event Term

A significant unexpected effect that affects the course of the study.

Organ System

• Eye Disorders

Collection Approach

• Systematic Assessment: Baseline and after surgery 1, 3, 6, and 12 months

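### Primary outcome 2 (endothelial cell density) has no rule for an eye whose cells cannot be counted, so eyes uncountable because the graft failed would drop out and bias it

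*Combined protocol and SAP*

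**What the plan says.** Section 3 (Outcome Measures, Primary Outcome Measure) lists "Endothelial Cell density" in cells/mm² as the second primary outcome. It is described only as "After surgery measurements", with "Time Frame: after surgery 1, 3, 6, and 12 months". Under Baseline Measure Title in section 2, "the change in the number of endothelial cells will be the primary outcome of the study", together with the change in visual acuity.

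The Statistical Analyses text in section 3 names repeated-measures ANOVA with Bonferroni comparisons for normally distributed measurements and Friedman with Wilcoxon otherwise. For associations, "Pearson and Spearman correlation test will be used in the correlation analysis". The title sets the question: "The Effect Of Preoperative Parameters On Success After Descemet Membrane Endothelial Keratoplasty (DMEK) Surgery".

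On numbers, section 2 says "A total of 60 participants are planned to participate in the study", and the analysis population in section 3 says "In total, we expect 60 participants to participate in the study".

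The plan does not give a method of counting cells, a criterion for a usable image, an entry for an uncountable cornea, a definition of graft failure or a rule for missing values. The participant flow in section 1 has only a blank box for exclusions from analysis and their reasons.

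**The concern.** A missed visit and an uncountable cornea are different problems. In the second, the participant attends and has an acuity and a corneal thickness, but the cell count is blank. If it is blank because the graft has failed, the absence depends on the value that would have been seen. Better attendance does not help, and a method that assumes data missing at random does not fully repair it.

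In their standard form, ANOVA and Friedman need a value at every visit analysed, and Wilcoxon and the correlations need complete pairs. An eye without a count therefore leaves each of them by default. The eyes removed would be among the most informative for the question in the title. Success is not defined, graft failure is not a listed outcome, and the complications outcome covers only the operation itself.

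**Working it through.** **The plan's own figure.** The sample size of 60 cannot be reproduced, because power, effect size, SD and dropout are not given. The point does not depend on it; 60 is used only as the number of eyes.

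**Inputs.** From the plan: n = 60 and p < 0.05 (taken as two-sided). Assumed, because the plan gives none of them: normal distributions; a true correlation of 0.40 between density and a preoperative parameter; an unreadable share of 5%, 10% or 15% (3, 6 or 9 eyes); and an SD of 500 cells/mm² where a result is put in cells. That counting needs a readable image is also an assumption.

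**1. Would any eye be affected?** The chance of at least one in 60 is 1 − (1 − f)^60. For f = 2% it is 1 − 0.98^60 = 70%. For f = 5% it is 1 − 0.95^60 = 95%.

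**2. Shift in the mean when exactly the lowest share f is lost.** For a normal variable the shift is φ(c)/(1 − f) SD, where c is the f-quantile:
- 5%: 0.1031/0.95 = 0.11 SD
- 10%: 0.1755/0.90 = 0.19 SD
- 15%: 0.2332/0.85 = 0.27 SD

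Simulation with 60 eyes gives 0.105, 0.191 and 0.269 SD. At an SD of 500 these are about 52, 96 and 135 cells/mm².

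**3. Effect on the correlation, same scenario (simulated).**

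| Eyes lost | Spearman, eyes dropped | Power | Spearman, lowest rank given | Power |
|---|---|---|---|---|
| 0 | 0.38 | 86% | – | – |
| 3 | 0.35 | 78% | 0.38 | 86% |
| 6 | 0.33 | 70% | 0.38 | 86% |
| 9 | 0.31 | 62% | 0.38 | 86% |

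The reference is 0.38, not 0.40, because Spearman on complete normal data runs slightly below the true Pearson value.

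**4. What if unreadability does not follow density so closely?** With 6 eyes unreadable:

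| Unreadable eyes | Mean shift | Dropped: Spearman, power | Lowest rank: Spearman, power |
|---|---|---|---|
| all 6 the lowest | 0.19 SD | 0.33, 70% | 0.38, 86% |
| 3 lowest, 3 unrelated | about 0.10 SD | 0.35, 75% | about 0.345, 78% |
| all 6 unrelated | none | 0.38, 82% | 0.31, 67% to 68% |

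**5. A different shape.** Step 2 is the largest shift for a given share only within the normal model. If failed grafts form a separate low group, the bias is f × (readable mean − failed mean). With assumed means of 1700 for readable and 300 to 500 for failed grafts, it is 0.05 × 1200 to 0.05 × 1400 = 60 to 70 cells/mm². At 10% it is 120 to 140, and at 15% it is 180 to 210.

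**The case against.** The strongest objection is that the size is built into the scenario. Removing exactly the lowest values assumes perfect dependence of readability on density, and nothing in the plan supports that. This stands: step 4 shows the bias halving and then disappearing as the dependence weakens. The figures in steps 2 and 3 are an upper end, not a forecast.

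The second objection is that giving the lowest rank can do harm. This also stands. When half of the unreadable eyes are unrelated to density, it recovers nothing in the coefficient. When all are unrelated, it is clearly worse than dropping them. An eye swollen at month 1 and clear at month 6 would also move from the bottom rank to an ordinary one and show a gain in density that never happened. The rule must therefore be limited to graft failure and must not replace the available-case analysis.

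A reader might go further and infer that every failed or swollen graft has no count, or that failure is invisible to the study. The documents support neither. A partly failing graft may still give a low reading. Visual acuity (primary) and central pachymetry (secondary) are taken at the same visits and can reflect failure, adverse-event reporting could note it, and the flow diagram would show exclusions. But none of these puts the eye back into the cell-density analysis.

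**Conclusion.** The gap is real and lies in a primary outcome. The plan makes no provision for an uncountable cornea, and its named tests drop such eyes. If the cause is graft failure and failed grafts have lower density than readable ones, the direction is known: mean density too high and correlations too weak.

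The size is not known. In the normal model, with 5% to 15% of eyes lost, it is at most about 0.10 to 0.27 SD on the mean. Spearman falls from 0.38 to between 0.35 and 0.31, and power from 86% to between 78% and 62%. The lower limit is no bias, when unreadability is unrelated to density or no eye is unreadable. All of this rests on an assumed unreadable share, an assumed correlation and the assumption that counting needs a readable image.

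The documents do not support saying that the reported mean will be overstated, or that a lowest-rank analysis should become the main one. They do support recording the reason for an absent count and fixing beforehand how failed grafts are handled.

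**What to change.** 1. Add one field per visit: density counted or uncountable and, if uncountable, whether because of graft failure, transient oedema or a technical problem. Report the number in each category at each visit.
2. State in the plan a definition of graft failure, chosen by the investigators and fixed before analysis.
3. Keep the available-case analysis. Beside it, pre-specify a second analysis with wording such as: *Eyes uncountable because of graft failure receive the lowest rank. Density is summarised by the median, and associations by Spearman, with this ranking. Values absent because of transient oedema or technical problems stay missing.*
4. For the comparison between visits, add a sensitivity analysis using the rank-based tests already named (Friedman and Wilcoxon), with failed eyes coded below every observed count. ANOVA and Pearson stay on observed values only.

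The cost is one data field, a failure definition and one extra analysis with methods the plan already names. The drawback is that the lowest-rank result loses accuracy if the reason for an absent count is misclassified. That is why both results and the counts by reason should be shown together.

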Number of Participants Affected

0

Number of Participants at Risk

0

▼ 5. Limitations and Caveats

Overall Limitations and Caveats

In our study, only Descemet membrane endothelial keratoplasty (DMEK) surgeries were included. However, Descemet's stripping automated endothelial keratoplasty (DSAEK) surgeries were not included, and no comparative study was performed.

▼ 6. Certain Agreements

Information indicating whether there exists an agreement between the sponsor or its agent and the principal investigators (unless the sponsor is an employer of the principal investigators) that restricts in any manner the ability of the principal investigators (PIs), after the completion of the study, to discuss the results of the study at a scientific meeting or any other public or private forum, or to publish in a scientific or academic journal information concerning the results of the study. This does not include an agreement solely to comply with applicable provisions of law protecting the privacy of participants.

Are all PIs Employees of Sponsor?

Definition: Indicate whether the principal investigator is an employee of the sponsor.

• Yes

PI Disclosure Restriction Type

There are no varying agreements.

▼ 7. Results Point of Contact

Point of contact for scientific information about the clinical study results information.

Name or Official Title *

Definition: [name] [name]

Organization Name *

Definition: Beyoglu Eye Research and Education Hospital

[contact]

[name]

Email: [contact]

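### Lens status and lens surgery are neither specified as variables nor used in the analysis, so lens-driven change in acuity or anterior chamber depth could be credited to DMEK or to a preoperative parameter

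*Combined protocol and SAP*

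**What the plan says.** The title sets the question: "The Effect Of Preoperative Parameters On Success After Descemet Membrane Endothelial Keratoplasty (DMEK) Surgery". The only description of the intervention, in the groups table, is "All participants underwent DMEK surgery". Nothing is said there about cataract removal before, with or after the graft.

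Under 2. Baseline Characteristics, the text reads: "Patients' age, gender, eye side, additional diseases, medications used and preoperative visual acuity values will be recorded at the beginning of the study". Lens status is not in that list.

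Under 3. Outcome Measures, the first primary outcome is "1.Visual Acuity (Snellen") and the second secondary outcome is "2. Anterior chamber depth (mm"). Both are changes from baseline, with "Time Frame: Baseline and after surgery 1, 3, 6, and 12 months". The remaining outcomes are endothelial cell density, keratometry, axial length, pachymetry, intraocular pressure and complications during surgery. None concerns the lens.

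The Statistical Analyses paragraph gives repeated-measures ANOVA (Friedman if not normal) over the preoperative, month 1 and month 6 measurements, with Bonferroni or Wilcoxon follow-up tests, plus Pearson and Spearman correlation. It names no covariate, stratum or exclusion. Section 4 confirms that there is one group only.

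Section 5 states that "only Descemet membrane endothelial keratoplasty (DMEK) surgeries were included". The next sentence contrasts DMEK with DSAEK. It does not address combined cataract surgery.

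**The concern.** ACD is measured from the cornea to the front of the lens. Replacing a natural lens with a thinner implant therefore changes ACD whatever the graft does. Cataract, and its removal, also changes acuity. With no comparison group, no control arm can cancel a lens effect, so any change from baseline will be read as the result of DMEK.

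The title question is exposed in a second way. The document does not say which variables will be correlated with outcome, but preoperative ACD is a plausible candidate because it is measured at baseline and the aim concerns preoperative parameters. Baseline ACD can differ between eyes with a natural lens and eyes with an implant, and acuity gain can differ between them too. A bivariate correlation cannot separate the parameter from lens status.

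At stake are one primary outcome, one secondary outcome and the answer to the study's stated question.

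**Working it through.** The plan gives no figure for the lens, so there is nothing of its own to reproduce on this point. Its 60 participants cannot be re-derived either, because effect size, SD, power and dropout are not stated. The sizes below are illustrations under stated assumptions, taking one eye per participant.

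**1. What is specified.** The baseline list in section 2 is not exhaustive. It omits keratometry, ACD, axial length, pachymetry and intraocular pressure, all of which section 3 measures at baseline. The text therefore supports saying that lens status is not a specified variable. It does not show that nobody will record it. The Statistical Analyses paragraph is clearer: no lens variable is used.

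**2. Shift in mean ACD change.**

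Shift = (share of eyes with a lens replacement between the two measurements) × (deepening per replacement).

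Assumed: share 0% to 50%, deepening 0.8 to 1.2 mm. Zero belongs in the range because eligibility is not shown.

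| Share (of 60) | at 0.8 mm | at 1.2 mm |
|---|---|---|
| 0% (0) | 0 | 0 |
| 10% (6) | 0.08 mm | 0.12 mm |
| 30% (18) | 0.24 mm | 0.36 mm |
| 50% (30) | 0.40 mm | 0.60 mm |

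This covers lens replacement only, not cataract formation.

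**3. Effect on tests and correlations.** Let a share f of eyes have a lens event that shifts the outcome by D standard deviations (SD) of the change score, with a true DMEK effect of zero. The bias in mean change is f × D SD. Now let a preoperative parameter differ by 1 SD between eyes with and without a lens event. The spurious correlation is

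r = f(1−f)D / √{[1 + f(1−f)D²][1 + f(1−f)]}.

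For f = 0.2 and D = 2: 0.32 / √(1.64 × 1.16) = 0.23.

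The rejection rates below come from 20,000 simulated studies of 60, with a two-sided 5% level and a paired t-test standing in for the planned ANOVA. Simulated mean correlations agree with the formula to within 0.005. Each range runs from D = 1 to D = 3.

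| f | Bias (SD) | p < 0.05, paired change | Spurious r | p < 0.05, correlation |
|---|---|---|---|---|
| 0% | 0 | about 5% | 0 | about 5% |
| 10% | 0.1 to 0.3 | 10% to 36% | 0.08 to 0.19 | 9% to 32% |
| 20% | 0.2 to 0.6 | 28% to 93% | 0.14 to 0.29 | 18% to 63% |
| 30% | 0.3 to 0.9 | 55% to about 100% | 0.17 to 0.34 | 26% to 79% |

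For scale, 60 participants give 80% power for a correlation of tanh[(1.960 + 0.842)/√57] = 0.35. The largest spurious correlation in the table is close to that. Where DMEK truly changes the outcome, as is hoped for acuity, the bias column is the relevant one, not the rejection rates.

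**4. Exposure window.** Section 1 plans 6 months of follow-up, section 3 lists visits to 12 months, and the Statistical Analyses paragraph names only months 1 and 6. The time available for later lens events is therefore unclear. Combined surgery would fall before month 1, and confounding by baseline lens status needs no follow-up time, so both arise under any of these windows.

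**The case against.** A reader might infer that the data will offer no way to detect a lens effect. The documents do not support that. The field for additional diseases could hold a cataract diagnosis, and section 4 has systematic adverse event assessment at baseline and every visit, classed under eye disorders. Serial ACD might itself show a jump as large as the one assumed. What stands against this defence is that neither field names the lens, an existing implant need not be listed as a disease, and neither field is used in the analysis.

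A reader might also infer that bias is certain. It is not. The flow chart has a box for people who fail the inclusion criteria, and section 3 refers to a protocol section of the registry record, so eligibility rules appear to exist outside this document. If entry was limited to eyes that already had an implant, cataract formation and removal could not occur and the main mechanism would disappear. This objection stands, and it is why the range starts at zero.

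Finally, if cataract follows from the surgery, its effect on acuity is part of the outcome after DMEK rather than contamination. This also stands. Lens surgery after DMEK therefore needs different handling from baseline lens status or concurrent surgery.

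**Conclusion.** The concern holds in conditional form. Lens status and lens surgery with or after DMEK are not specified variables and do not enter an analysis made up of unadjusted pre/post tests and bivariate correlations in one group. If eyes with a natural lens or combined cataract surgery are included, lens-driven change could be credited to DMEK, and a correlation with acuity gain could reflect lens status.

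The size is 0 to 0.6 mm in mean ACD change. It rests on two assumptions, the share of eyes affected and the deepening per eye, neither of which the documents give. The effect on acuity in its own units cannot be sized from the documents; the SD-unit figures are illustrative only.

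**What to change.** Record three items: baseline lens status (natural lens or implant), lens surgery at the time of DMEK, and the date of any later lens surgery.

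In the analysis section:

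- Report ACD change, acuity change and the correlations with preoperative parameters stratified by, or adjusted for, baseline lens status and concurrent lens surgery.
- For lens surgery after DMEK, keep all eyes in the main acuity analysis and add a sensitivity analysis that leaves out measurements taken after that surgery.
- For ACD, show eyes with a lens change separately.
- State the eligibility rule on lens status. If only eyes with an implant were entered, saying so removes most of the problem.
- Reconcile the follow-up window across section 1, section 3 and the Statistical Analyses paragraph.

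The cost is a few data fields and one stratified table. The planned 60 does not change, but strata will be smaller than 60 and their estimates less precise. The sensitivity analysis selects on an event after surgery, so it should be read as supportive only.

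### The planned ANOVA and Friedman tests use only participants measured at every analysed visit, and the plan has no rule for missing visits

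*Combined protocol and SAP*

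**What the plan says.** Section 3 (Outcome Measures), under Statistical Analyses, names the main test and its visits: "Variance analysis (ANOVA) will be used in the statistical analysis of preoperative and postoperative 1st and 6th months", provided the measurements are normally distributed, with Bonferroni comparisons afterwards. For other data, "Friedman test will be used in the statistical analysis of measurements that do not show normal distribution", followed by Wilcoxon tests.

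The outcome list in the same section has a wider schedule. Visual acuity and the secondary measurements carry "Time Frame: Baseline and after surgery 1, 3, 6, and 12 months". Endothelial cell density, the second primary outcome, has postoperative values only: "Time Frame: after surgery 1, 3, 6, and 12 months".

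Section 2 gives the planned size: "A total of 60 participants are planned to participate in the study". The field for the number analysed, in section 3, repeats it: "In total, we expect 60 participants to participate in the study".

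The plan defines no analysis set and gives no expected dropout rate, missing-data rule, imputation method or missing-data sensitivity analysis. The section 1 flow chart has blank fields for loss to follow-up and exclusion from analysis, and that section promises to report the numbers at the start and end of the study.

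**The concern.** Friedman ranks each participant's values across visits, so a participant with a gap cannot enter in the standard form. Classical repeated-measures ANOVA likewise works on complete rows. The choice of test therefore brings in complete-case analysis without the plan saying so. Making the visit schedule consistent would not remove this; adding visits to the test would increase the loss.

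There are two consequences. Values already collected from partly observed participants are discarded. And if participants with a gap differ from the rest, the means at each visit describe a selected group. The second matters most for endothelial cell density, because its postoperative level, rather than a change from baseline, is the listed primary outcome.

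**Working it through.** **The plan's own figure.** The plan says "The required sample size was determined by power analysis based on previous studies" but gives no effect size, SD, correlation, power or dropout allowance, so 60 cannot be reproduced. The usual G*Power within-subject form (3 visits, alpha 0.05, noncentrality f² × N × 3 / (1 − ρ)) gives a required N from 8 to 362 over f = 0.10, 0.25, 0.40, ρ = 0.3, 0.5, 0.7 and power 0.80, 0.90, 0.95. Nothing in the document picks out one combination.

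**Loss of records.** Inputs are N = 60 and the two postoperative visits in the written test (months 1 and 6). The missingness rate m per visit is an assumption, taken as independent between visits. Complete records = 60 × (1 − m)²:

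- m = 5%: 60 × 0.9025 = 54.2
- m = 10%: 60 × 0.81 = 48.6
- m = 15%: 60 × 0.7225 = 43.4
- m = 20%: 60 × 0.64 = 38.4

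If the test were extended to all four postoperative visits, 60 × (1 − m)⁴ gives 48.9 at 5% and 39.4 at 10%. That is not the test as written.

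**Power, for illustration.** Suppose 60 gave exactly 80% power for three visits (f = 0.166, ρ = 0.5, both assumed). Power is then about 75% with 54 complete records and 71% with 49.

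**Bias when missingness follows the month-1 value.** The assumed set-up has three visits, a correlation of 0.6 between any two, and 15% of month-6 values missing. The chance of missing is logistic in the month-1 value, with low values more likely to be followed by a gap. Complete-case bias, in SD units:

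| Logistic slope | Month-1 mean | Month-6 mean |
|---|---|---|
| 0.5 | +0.07 | +0.04 |
| 1.0 | +0.13 | +0.08 |
| 1.5 | +0.17 | +0.10 |

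A simple relation explains this. If selection acts on month 1 and shifts its mean by δ, the other two means shift by about 0.6 × δ; for example 0.6 × 0.17 = 0.10. The changes then follow:

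- Preoperative to month 1: 0.4 × δ, or +0.03 to +0.07.
- Preoperative to month 6: 0.6 × δ − 0.6 × δ = 0.
- Month 1 to month 6: −0.4 × δ, or −0.03 to −0.07.

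A likelihood analysis of all available values has bias near 0 throughout this set-up. When missingness was completely at random, it was up to about 7% more precise than complete cases.

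**Direction.** A second simulation used correlation 0.5, 15% missing at month 6 and a true preoperative-to-month-6 change of 0.80 SD. The complete-case change was 0.87 when poor month-6 values tended to be missing, 0.80 when missingness was unrelated to outcome, and 0.73 when good values tended to be missing.

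**Missingness that depends on the unseen value.** In a four-visit simulation with 18% incomplete and dropout driven by the current value, the true first-to-last change was −0.30 SD. Complete cases gave −0.265 and likelihood gave −0.224. The mixed model does not solve this case and was further from the truth for change.

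**The case against.** The strongest reply is that the tests compare visits within the same people, so shifts in level largely cancel. That stands for the preoperative-to-month-6 change when missingness depends only on the month-1 value. It does not stand for the changes into or out of month 1, or for postoperative cell density reported as a level.

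A second reply is that the document never says participants will be dropped, foresees losses in its flow chart, and names Wilcoxon and correlation tests that could use all available pairs. This is fair: complete-case analysis is inferred from the standard form of the tests. But reporting losses is not a rule for analysing them. Pairwise tests on all available pairs would also rest on different participants from the overall test.

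Third, a mixed model is no cure if values are missing because of what they would have been, for example an unreadable endothelial image. This stands, and it is why a separate sensitivity analysis is needed.

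A reader might go further and infer that the planned tests favour participants with good outcomes. The document gives no rate, pattern or reason for missed visits, and the sign of the bias follows from the assumed mechanism. A reader might also infer that any missed visit removes a participant. As written, a missed month 3 or month 12 removes nobody.

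**Conclusion.** The point holds for the three visits in the written test. The named tests default to participants with complete data at those visits, and the plan neither acknowledges this nor says how gaps are handled. The analysed number would be about 54 or 49 of 60 at an assumed 5% or 10% missing per postoperative visit.

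Bias is possible but not established. Under missingness driven by earlier values, it was up to about 0.17 SD in a visit mean and 0.07 SD in a change in the scenarios above, with a sign that depends on why visits are missed. Every rate, correlation and mechanism here is an assumption. This goes beyond a missing policy statement, because a readily available method uses the partial records and needs a weaker assumption. It should be changed, but it does not invalidate the study.

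**What to change.** - Make the primary repeated-measures analysis a linear mixed model with visit as a categorical effect and an unstructured within-participant covariance. Include every participant with at least one measurement, and transform the outcome if residuals are skewed. This also removes the sphericity assumption of the classical ANOVA.
- Report the number of participants contributing at each visit, with reasons for missing values.
- Keep the planned ANOVA or Friedman test on complete cases as a sensitivity analysis.
- Add a sensitivity analysis for missingness that depends on the unseen value, for example by shifting the missing values by a range of deltas.
- Reconcile the visits in the written test with those in the outcome definitions, since that decides which gaps matter.

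The cost is SAP wording and slightly more analysis work. The mixed model relies on data being missing at random. This cannot be verified, but it is weaker than the completely-at-random assumption that complete-case analysis generally needs.
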